10.3 Visit 3 (Day 3, telephone)

1. Record any Adverse Events
2. Symptom assessment
3. Skindex-16

10.4 Visit 4 (Day 8)Unblinded investigator:

1. Record changes to concomitant medications.
2. Record any Adverse Events
3. Symptom assessment
4. Record Skindex-16
5. Photography of treatment area.

Blinded investigator:

6. Perform abbreviated physical examination.
7. Perform AK count
8. Record LSR

10.5 Visit 5 (Day 15, telephone)

1. Record any Adverse Events
2. Symptom assessment
3. Skindex-16

10.6 Visit 6 (Day 29)Unblinded investigator:

1. Record changes to concomitant medications.
2. Record any Adverse Events.
3. Symptom assessment
4. Skindex-16
5. Photography of treatment area.

Blinded investigator:

6. Perform abbreviated physical examination
7. Perform an AK count (blinded investigator)
8. Perform a local skin response assessment (blinded investigator)

10.7 Visit 7 (Day 84)

Unblinded investigator:

1. Record changes to concomitant medications.
2. Record any Adverse Events.
3. Symptom assessment
4. Skindex-16
5. Photography of treatment area.

Blinded investigator:

6. Perform abbreviated physical examination
7. Perform an AK count (blinded investigator)
8. Perform a local skin response assessment (blinded investigator)

10.8 Early Withdrawal Visit

Unblinded investigator:

1. Record changes to concomitant medications.
2. Perform complete physical examination.
3. Record any Adverse Events.
4. Symptom assessment
5. Record Skindex-16
6. Photography of treatment area.

Blinded investigator:

7. Perform AK count
8. Record LSR

11 ADVERSE EVENTS REPORTING AND DOCUMENTATION

11.1 Adverse Events

An adverse event (AE) is any untoward medical occurrence in a clinical investigation of a patient administered a pharmaceutical product and that does not necessarily have a causal relationship with the treatment. An AE is therefore any unfavorable and unintended sign (including an abnormal laboratory finding), symptom or disease temporally associated with the administration of an investigational product, whether or not related to that investigational product. An unexpected AE is one of a type not identified in nature, severity, or frequency in the current Investigator's Brochure or of greater severity or frequency than expected based on the information in the Investigator's Brochure.

The Investigator will probe, via discussion with the subject, for the occurrence of AEs during each subject visit and record the information in the site's source documents. Adverse events will be recorded in the patient CRF. Adverse events will be described by duration (start and stop dates and times), severity, outcome, treatment and relation to study drug, or if unrelated, the cause.

AE Severity

The National Cancer Institute's Common Terminology Criteria for Adverse Events (CTCAE) Version 4.0 should be used to assess and grade AE severity, including laboratory abnormalities judged to be clinically significant. The modified criteria can be found in the study manual. If the event is not covered in the modified criteria, the guidelines shown in Table 1 below should be used to grade severity. It should be pointed out that the term "severe" is a measure of intensity and that a severe AE is not necessarily serious.

Table 1. AE Severity Grading

Severity (Toxicity Grade)	Description
Mild (1)	Transient or mild discomfort; no limitation in activity; no medical intervention or therapy required. The subject may be aware of the sign or symptom but tolerates it reasonably well.
Moderate (2)	Mild to moderate limitation in activity, no or minimal medical intervention/therapy required.
Severe (3)	Marked limitation in activity, medical intervention/therapy required, hospitalizations possible.
Life-threatening (4)	The subject is at risk of death due to the adverse event as it occurred. This does not refer to an event that hypothetically might have caused death if it were more severe.

AE Relationship to Study Drug

The relationship of an AE to the study drug should be assessed using the following the guidelines in Table 2.

Table 2. AE Relationship to Study Drug

Relationship to Drug	Comment
Definitely	Previously known toxicity of agent; or an event that follows a reasonable temporal sequence from administration of the drug; that follows a known or expected response pattern to the suspected drug; that is confirmed by stopping or reducing the dosage of the drug; and that is not explained by any other reasonable hypothesis.

Probably	An event that follows a reasonable temporal sequence from administration of the drug; that follows a known or expected response pattern to the suspected drug; that is confirmed by stopping or reducing the dosage of the drug; and that is unlikely to be explained by the known characteristics of the subject's clinical state or by other interventions.
Possibly	An event that follows a reasonable temporal sequence from administration of the drug; that follows a known or expected response pattern to that suspected drug; but that could readily have been produced by a number of other factors.
Unrelated	An event that can be determined with certainty to have no relationship to the study drug.

11.2 Serious Adverse Events (SAE)

An SAE is defined as any AE occurring at any dose that results in any of the following outcomes:

- death
- a life-threatening adverse event
- inpatient hospitalization or prolongation of existing hospitalization
- a persistent or significant disability/incapacity
- a congenital anomaly/birth defect

Other important medical events may also be considered an SAE when, based on appropriate medical judgment, they jeopardize the subject or require intervention to prevent one of the outcomes listed.

11.2.1 Serious Adverse Event Reporting

Study sites will document all SAEs that occur (whether or not related to study drug) per [UCSF IRB Guidelines](#). The collection period for all SAEs will begin after informed consent is obtained and end after procedures for the final study visit have been completed.

In accordance with the standard operating procedures and policies of the local Institutional Review Board (IRB), the site investigator will report SAEs to the IRB.

12 DISCONTINUATION AND REPLACEMENT OF SUBJECTS

12.1 Early Discontinuation of Study Drug

A subject may be discontinued from study treatment at any time if the subject or the investigator, or the Sponsor feels that it is not in the subject's best interest to continue. The following is a list of possible reasons for study treatment discontinuation:

Subject withdrawal of consent (or assent)

Subject is not compliant with study procedures

Adverse event that in the opinion of the investigator would be in the best interest of the subject to discontinue study treatment

Protocol violation requiring discontinuation of study treatment

Lost to follow-up

Sponsor request for early termination of study

Positive pregnancy test (females)

If a subject is withdrawn from treatment due to an adverse event, the subject will be followed and treated by the Investigator until the abnormal parameter or symptom has resolved or stabilized.

All subjects who discontinue study treatment should come in for an early discontinuation visit as soon as possible and then should be encouraged to complete all remaining scheduled visits and procedures.

All subjects are free to withdraw from participation at any time, for any reason, specified or unspecified, and without prejudice.

Reasonable attempts will be made by the investigator to provide a reason for subject withdrawals. The reason for the subject's withdrawal from the study will be specified in the subject's source documents Refer to Section 10 for early termination procedures.

12.2 Withdrawal of Subjects from the Study

A subject may be withdrawn from the study at any time if the subject or the investigator , or the Sponsor feels that it is not in the subject's best interest to continue.

All subjects are free to withdraw from participation at any time, for any reason, specified or unspecified, and without prejudice.

Reasonable attempts will be made by the investigator to provide a reason for subject withdrawals. The reason for the subject's withdrawal from the study will be specified in the subject's source documents. As noted above, subjects who discontinue study treatment early (i.e., they withdraw prior to Visit 7) should have an early discontinuation visit. Refer to Section 10 for early termination procedures. Subjects who withdraw should be encouraged to come in for a final visit (and the procedures to be followed would include those for their next scheduled visit).

12.3 Replacement of Subjects

Subjects who withdraw from the study treatment will not be replaced.

Subjects who withdraw from the study will not be replaced.

13 PROTOCOL VIOLATIONS

A protocol violation occurs when the subject or investigator fails to adhere to significant protocol requirements affecting the inclusion, exclusion, subject safety and primary

endpoint criteria. Protocol violations for this study include, but are not limited to, the following:

Failure to meet inclusion/exclusion criteria

Use of a prohibited concomitant medication

Failure of compliance with treatment regimen as described for assigned treatment arm

Failure to comply with Good Clinical Practice (GCP) guidelines will also result in a protocol violation.

When a protocol violation occurs, it will be discussed with the investigator and a Protocol Violation Form detailing the violation will be generated. This form will be signed by the Investigator. A copy of the form will be filed in the site's regulatory binder.

14 DATA SAFETY MONITORING

Due to the scope of this study, there will be no formal Data Safety Monitoring Board (DSMB) or Data Monitoring Committee (DMC). This is an open-label, single-center study for an FDA-approved medication, and the investigator will have access to all study data.

15 STATISTICAL METHODS AND CONSIDERATIONS

Prior to the analysis of the final study data, a detailed Statistical Analysis Plan (SAP) will be written describing all analyses that will be performed. The SAP will contain any modifications to the analysis plan described below.

15.1 Data Sets Analyzed

All eligible patients who are enrolled in the study and receive at least one dose of the study drug (the Safety Population) and who have had at least one post-baseline safety evaluation will be included in the safety analysis.

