4 STUDY DESIGN

4.1 Study Overview

This is a randomized (1:1:1) controlled trial with parallel group design. Thirty adult subjects are planned; with 10 subjects in each of three treatment arms.

Screening data will be reviewed to determine subject eligibility. Subjects who meet all inclusion criteria and none of the exclusion criteria will be entered into the study.

The following medications and devices will be used:

- (1) Aminolevulinic acid HCl topical solution 20% (Levulan Kerastick)
- (2) BLU-U blue light phototherapy illuminator

Three treatment arms to be compared are as follows:

- A. Conventional arm:** Acetone preparation, ALA topical application, 1 hour incubation, 16:40 BLU-U exposure, application of sunscreen.
- B. Combination arm:** Acetone preparation, ALA topical application, 15 minute incubation, 16:40 BLU-U exposure, application of sunscreen, 45 minute daylight exposure.
- C. Daylight arm:** Acetone preparation, ALA topical application, 15 minute incubation, application of sunscreen, 1 hour daylight exposure.

Total duration of subject participation will be up to 115 days. Total duration of the study is expected to be 16 months.

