8.4.1 Dosage/Dosage Regimen

Aminolevulinic acid HCl topical solution 20% (Levulan Kerastick) will be applied topically once by a healthcare provider on the day of treatment. One Levulan Kerastick will be applied to the treatment area on the face or scalp. Care will be taken to avoid the eyes and mouth.

Treatment arms are as follows:

- A. Conventional arm:** Acetone preparation, ALA topical application, 1 hour incubation, 16:40 BLU-U exposure, application of sunscreen.
- B. Combination arm:** Acetone preparation, ALA topical application, 15 minute incubation, 16:40 BLU-U exposure, application of sunscreen, 45 minute daylight exposure.
- C. Daylight arm:** Acetone preparation, ALA topical application, 15 minute incubation, application of sunscreen, 1 hour daylight exposure.

Due to photosensitivity, subjects should avoid sunlight, tanning beds, and any prolonged or intense light exposure for 40 hours after application of ALA HCl, outside of the assigned treatment regimen. Subjects should not wash or clean their faces until all steps of treatment have been completed.

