10.2 Visit 2 (Day 1, may be combined with Screening)

Unblinded investigator:

1. Randomization to treatment arms (1:1:1). Investigator will use sequential envelopes with randomly prefilled treatment arms. Envelopes will be filled in batches of three (nine patients) to ensure even allocation between arms during the course of treatment.
2. Perform and record vital signs.
3. Concomitant medications and Adverse Events review.

Blinded investigator:

4. Perform abbreviated physical examination.
5. Perform an AK count
6. Perform a pre-treatment local skin response assessment
7. Curette any hypertrophic AK
8. Application of ALA

Unblinded investigator:

9. Monitor ALA incubation duration depending on treatment arm
10. Light exposure (BLU-U and/or sunlight, depending on treatment arm)
11. Symptom assessment. All subjects will have symptom assessments at 15, 30, 45, 60, and 75 minutes (Table 2).
12. Skindex-16
13. Record any Adverse Events.
14. Photography of treatment area.

Blinded investigator:

15. Perform a post-treatment local skin response assessment

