15.4 Analysis of Secondary Endpoints

Efficacy and tolerability data will be summarized by each secondary endpoint.

Symptom level over time during the treatment period will be graphed for visualization along the three axes of pain, stinging/burning, and itching/pruritus as well as a composite symptom score. Peak symptom level during the treatment period and pain at the end of treatment exposure will be compared between the conventional treatment arm (A), the combination treatment arm B), and the daylight treatment arm (C), with unpaired t-tests.

Percent reduction in the number of actinic keratoses and proportions of patients with partial and complete clearance of actinic keratoses will be presented descriptively and visualized as histograms. We will compare the percent reduction in the number of AKs and the proportions of patients with clearance between the conventional treatment arm (A) and the combination treatment arm B), and between the conventional treatment arm (A) and the daylight treatment arm (C), using unpaired t-tests.

All analyses will be based on the intent-to-treat (ITT) population. In the ITT population, patients will be counted in the treatment group upon randomization, regardless of receiving any dose of study medication. For efficacy analysis, all missing values due to patient early termination from the study will be imputed using last observation carried forward (LOCF) method, as appropriate. For each patient, the Baseline values will be defined as those values recorded at Day 1 prior to dosing. Patients who are lost-to-follow-up after Baseline will be included to the ITT population carrying forward their Baseline values.

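### Read literally, Section 15.1 leaves a treated subject later found ineligible out of the adverse-event summary, and it conflicts with the statement that all analyses use the ITT population

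*Combined protocol and SAP*

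**What the plan says.** Section 15.1 sets two joint conditions for the safety analysis. The first is "All eligible patients who are enrolled in the study and receive at least one dose of the study drug (the Safety Population". The second is that these are patients "who have had at least one post-baseline safety evaluation will be included in the safety analysis". The population label follows the first condition, so the named population and the set actually analysed are not the same.

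Section 13 gives an open list of protocol violations that includes "Failure to meet inclusion/exclusion criteria". The consequence it states is discussion with the investigator and a signed, filed form. It does not mention analysis sets.

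The synopsis (Statistics) and Section 15.4 both state: "All analyses will be based on the intent-to-treat (ITT) population". In that population "patients will be counted in the treatment group upon randomization, regardless of receiving any dose of study medication". Eligibility plays no part in this definition.

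**The concern.** A safety set normally contains everyone exposed to the treatment, because exposure is what puts a subject at risk. Section 15.1 adds eligibility to exposure. ALA is applied once, so an eligibility failure found afterwards cannot undo the exposure. It can only move the subject out of the table.

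Late discovery is plausible here. Screening and Day 1 may be one visit, and Section 10.2 lists the Day 1 AK count after randomization, although the lesion count is an inclusion criterion. The Visit 1 list in Section 10.1 omits the AK count that Section 9.1.6 and Appendix I place at Screening.

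Eligibility itself is not stated uniformly. The 14-day period without other AK treatment runs back from screening in the synopsis and from enrollment in Section 6.2. If enrollment comes after screening, a subject treated less than 14 days before screening but more than 14 days before enrollment fails one version and passes the other. Those passages need to be reconciled. Until then, membership of the safety set could depend on which one is read.

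What is at stake is the adverse-event summary by arm. In arms of 10, one subject can change what it shows.

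**Working it through.** **Step 1. Set the rules side by side.** The plan gives no figure on this point to reproduce, so the check is who is counted under each rule.

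| Subject | 15.1, literal | 15.1, *eligible* taken as judged at entry | ITT (synopsis, 15.4) | All treated |
|---|---|---|---|---|
| Treated, eligible, evaluated after baseline | in | in | in | in |
| Treated, later found ineligible, evaluated | **out** | in | in | in |
| Treated, eligible, no post-baseline evaluation | out | out | in | in |
| Randomized, never treated | out | out | in | out |

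The second row is the problem: the rules give different answers and the documents do not choose between them. The fourth row shows that the ITT sentence does not supply a proper safety set either, because it counts subjects who were never exposed. ITT also groups by randomization, while Section 15.1 gives no grouping rule and Section 13 foresees departures from the assigned regimen.

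**Step 2. How much the post-baseline condition can do.** ALA "will be applied topically once by a healthcare provider on the day of treatment", and on the same day "All subjects will have symptom assessments at 15, 30, 45, 60, and 75 minutes (Table 2". Section 5.3 names adverse-event reporting and physician evaluation as the safety evaluations. Section 10.2 schedules adverse-event recording and a post-treatment skin assessment by the blinded investigator on Day 1. A treated subject without any post-baseline evaluation should therefore be rare, and the eligibility word is the condition that matters.

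**Step 3. Size.** Section 4.1 plans 30 subjects, 10 per arm.

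- Share of an arm's safety denominator removed by one exclusion: 1/10 = 10%.
- Share of the trial: 1/30 = 3.3%.

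Illustration, assuming one treated, ineligible subject who has the only event of a given kind in the arm (first row) or in the trial (second row), with exact (Clopper-Pearson) 95% intervals:

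| | 15.1, literal | All treated |
|---|---|---|
| Arm | 0/9 = 0% (0 to 33.6%) | 1/10 = 10% (0.3 to 44.5%) |
| All arms | 0/29 = 0% (0 to 11.9%) | 1/30 = 3.3% (0.1 to 17.2%) |

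For zero events the upper limit is 1 − 0.025^(1/n): n = 9 gives 0.336 and n = 29 gives 0.119.

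The power statement in Section 15.6 concerns pain and does not depend on the safety set.

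**The case against.** The strongest reply is that *eligible* was never meant as a retrospective filter. Section 4.1 says "Subjects who meet all inclusion criteria and none of the exclusion criteria will be entered into the study", and Section 8.1 likewise speaks of eligible patients being randomized. On that usage the word describes how subjects came into the study, and nobody leaves the safety set later. This reading is reasonable and may be what was intended. Section 15.1 does not say so, however, and its literal reading remains open.

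The ITT sentence would also keep the subject. That is true if it governs safety, but it sits with the efficacy text and contradicts the specific safety definition. It leaves a conflict unresolved.

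A reader might infer that harm in such a subject disappears from the trial. The documents do not support that:

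- Adverse events are collected throughout (Section 9.1.11).
- SAEs are documented whether or not related to study drug, and reported to the IRB (Sections 11.2.1 and 17.2).
- Section 2.1 describes the risks as mainly local site reactions. Pain, stinging/burning and itching are primary endpoints and local skin reaction is a secondary one. These are analysed outside Section 15.1 and, on the natural reading, in the ITT population.

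A reader might also infer that ineligible subjects are in general those most likely to react. Only one criterion supports this, the exclusion in Section 6.3 of skin disease that treatment may worsen. The lesion-count, washout and consent criteria carry no such implication.

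Finally, the arm-level example is constructed. The documents give no probability for it, and its two intervals overlap widely.

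**Conclusion.** The point holds as a minor defect of definition. On its literal wording, Section 15.1 takes a treated subject later found ineligible out of the summarised adverse-event results. The synopsis and Section 15.4 imply the opposite, and the documents do not say which applies. The same subject could then count in the primary tolerability comparison and be absent from the safety summary.

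The effect is 10% of an arm's safety denominator for each such subject. The change from 1/10 to 0/9 follows only if that subject also had the arm's only event of that kind.

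Two stronger conclusions are not supported. The plan nowhere states that subjects found ineligible will be removed. Section 13 lists failed eligibility as a kind of violation, and does not predict that it will occur or attach an exclusion from analysis. The SAP promised in Section 15 could settle the matter, but the present text does not.

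**What to change.** In Section 15.1, define the safety set as all subjects to whom any ALA was applied, with no condition on eligibility or on a later evaluation, grouped by the light regimen actually received. Attach the name of the safety population to that whole definition.

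In the synopsis and Section 15.4, limit the ITT sentence to the efficacy and tolerability endpoints so that it no longer competes with Section 15.1. Carry both changes into the SAP.

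The cost is one rewritten sentence and one short qualification made in two places. Sample size, power, visits and data collection are unchanged. Subjects found ineligible after treatment can still be identified through the violation forms in Section 13, so a listing that flags them needs no new data.

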15.2 Demographic and Baseline Characteristics

The following demographic variables at screening will be summarized by dose level: race, gender, age, height and weight.

